5.1.4 Complementary outputs

Additional analyses by gender will be provided in Appendix 15 of the CSR.

Immunogenicity analyses:

- hSBA GMTs and 95% CI at each time point – Per-Protocol Analysis Set
- Vaccine seroresponse against meningococcal serogroups A, C, Y, and W measured by hSBA and 95% CI – Per-Protocol Analysis Set
- rSBA GMTs and 95% CI at each time point – Per-Protocol Analysis Set
- Vaccine seroresponse against meningococcal serogroups A, C, Y, and W measured by rSBA and 95% CI – Per-Protocol Analysis Set

Safety analyses:

Safety overview after vaccine injection –Safety Analysis Set

Some demographics tables will be also described by MenC primed background.

5.2 Analysis Sets

Three analysis sets will be used: the Full Analysis Set (FAS), the Per-Protocol Analysis Set (PPAS), and the Safety Analysis Set (SafAS).

5.2.1 Full Analysis Set

The FAS is defined as the subset of subjects who received at least 1 dose of the study vaccine and had a valid post-vaccination serology result. All subjects will be analyzed according to the treatment group to which they were randomized.

5.2.2 Per-Protocol Analysis Set

The PPAS is a subset of the FAS. The subjects presenting with at least one of the following relevant protocol deviations will be excluded from the PPAS:

- Subject did not meet all protocol-specified inclusion criteria or met at least one of the protocol-specified exclusion criteria
- Subject did not receive vaccine
- Subject received a vaccine other than the one that he/she was randomized to receive
- Preparation and/or administration of vaccine was not done as per-protocol
- Subject did not receive vaccine in the proper time window
- Subject did not provide post-dose serology sample in the proper time window or a post-dose serology sample was not drawn. The time windows are defined as D30 to D44 post-vaccination.

- Subject received a protocol-prohibited Category 2 or Category 3 therapy/medication/vaccine
- Subject's serology sample did not produce a valid test result , i.e. results equal to 'NR' or missing for all 4 serogroups (at post-vaccination)
- Subject had other protocol deviations that affected the subject's immune response, as determined by the clinical team before locking the database

5.2.3 Safety Analysis Set

The SafAS is defined as those subjects who have received at least 1 dose of the study vaccine and have any safety data available. All subjects will have their safety analyzed according to the vaccine they actually received. If the vaccine received by a subject does not correspond to any study group, the subject will be excluded from the SafAS. The corresponding safety data will be presented in separate listings.

5.2.4 Populations Used in Analyses

All immunogenicity analyses will be performed on the PPAS. Additional immunogenicity analyses will be performed for exploratory purposes on the FAS. In the FAS, subjects will be analyzed by the vaccine group to which they were randomized.

The safety analyses will be performed on the SafAS. Subjects will be analyzed according to the vaccine they actually received.

5.3 Handling of Missing Data and Outliers

5.3.1 Safety

No replacement will be done. In subject listings, partial and missing data will be clearly indicated as missing.

5.3.1.1 Immediate

For unsolicited non-serious systemic AEs, a missing response to the "Immediate" field is assumed to have occurred after the 30-minute surveillance period and will not be imputed.

For SAEs, missing or partially missing elapsed time from last vaccination recorded if within 24 hours will remain missing and not be imputed. Such SAEs will not be considered as immediate.

5.3.1.2 Causality

Missing causality (relationship) for unsolicited non-serious AEs and SAEs will be considered at the time of analysis as related to vaccination.

5.3.1.3 Measurements

Partially missing temperatures will be handled as described in [Section 4.4.1.1.1](#)

5.3.1.4 Intensity

For solicited reactions, missing intensities will be handled as described in [Section 4.4.1.1.1](#). For unsolicited non-serious AEs, missing intensities will remain missing and will not be imputed.

5.3.1.5 Start Date and Stop Date

Missing or partially missing start dates for unsolicited AEs will remain missing and not be imputed. If either the start or stop date is missing or partially missing, the time of onset will be considered to be missing. Nevertheless unsolicited AEs with missing time of onset will be included in analyses according to the visit collected.

Missing or partially missing stop dates for AEs (solicited reactions and unsolicited AEs) will remain missing and not be imputed.

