**9.3.2.3.3 Unsolicited Non-serious Adverse Events from D0 to Day 30 after Vaccination**

In addition to recording solicited reactions, parents/legally acceptable representatives will be instructed to record any other medical events that may occur during the 30 day period after vaccination. Space will be provided in the diary card for this purpose.

For each unsolicited non-serious AE, the following information is to be recorded:

- Start and stop datesa
- Intensity of the event:
  - For measurable unsolicited non-serious AEs that are part of the list of solicited reactions, the size of the AE as well as the temperature for fever will be collected and analyzed based on the corresponding scale used for solicited reactions (see [Table 9.1](#) and [Table 9.2](#))
  - Other unsolicited non-serious AEs will be classified according to the following intensity scale:
    - Grade 1: No interference with activity
    - Grade 2: Some interference with activity
    - Grade 3: Significant; prevents daily activity
- Action taken for each AE, if any (e.g., medication)

The action taken by the parent/legally acceptable representative to treat any **unsolicited AEs** will be classified in the CRF using the following scale:

0: None

1: Medication (self-medication with an existing prescription or over-the-counter medication)

2: Health care provider contact (no new medication prescribed)

---

a The stop date of all related AEs will be actively solicited. For other events, the investigator will provide the stop date when it becomes available. AEs for which no stop date was obtained during the course of the trial will be considered as ongoing at the end of the trial.

3: Health care provider contact and prescription of a new medication (health care provider instructed subject to take a new medication, either an over-the-counter medication or one requiring a written prescription)

- Whether the AE led to discontinuation
- Whether the AE was related to vaccination (for unsolicited systemic AEs)

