4.4.1.2.3 Last Vaccination

Last vaccination before an unsolicited non-serious AE is derived from the visit numbers provided in the clinical database and is calculated as follows:

- If an unsolicited non-serious AE has a non-missing visit number, the visit number should be used to determine the last vaccination before the unsolicited non-serious AE

If the visit number is missing, then the start date should be used to determine the last vaccination before the unsolicited non-serious AE

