4.4.1.2.4 Time of Onset

Time of onset is derived from the start date of the unsolicited non-serious AE provided in the clinical database and the date of last vaccination:

- start date of the unsolicited non-serious AE – date of previous vaccination

The time of onset should be considered as missing only if one or both of the dates are missing or partially missing.

The unsolicited non-serious AEs will be analyzed “Within 30 days”, which corresponds to AEs with a time of onset between 0 and 30 days after vaccination or missing. An AE with missing time of onset will be considered to have occurred just after the vaccination indicated by the visit number, so will be included in these tables.

Note: Unsolicited non-serious AE that occurred before vaccination (negative time of onset) or with a time of onset higher than defined above will not be included in analysis, but will be listed separately.

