4.4.1.2.5 Duration

Duration is derived from the start and stop dates of the unsolicited non-serious AE provided in the clinical database:

- stop date of unsolicited non-serious AE - start date of unsolicited non-serious AE + 1.

The duration should be considered as missing only if one or both of the start and stop dates of the unsolicited non-serious AE is missing or partially missing.

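### SAP 5.3.1.5 discards a known AE onset when only the stop date is missing, against SAP 4.4.1.2.4, and the non-serious AE tables stop at Day 30 although the endpoint runs to Visit 2

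*SAP*

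**What the plan says.** **Onset.** SAP 4.4.1.2.4 defines time of onset for an unsolicited non-serious AE as its start date minus the date of the preceding vaccination, and adds: "The time of onset should be considered as missing only if one or both of the dates are missing or partially missing". The two dates in that formula are the AE start and the vaccination. SAP 5.3.1.5 gives another rule: "If either the start or stop date is missing or partially missing, the time of onset will be considered to be missing". The stop date otherwise matters in SAP 4.4.1.2.5, where duration is "missing only if one or both of the start and stop dates of the unsolicited non-serious AE is missing" or partially so.

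**What follows from a missing onset.** SAP 4.4.1.2.4 places onsets from Day 0 to Day 30, and missing onsets, in the 30-day analysis: "An AE with missing time of onset will be considered to have occurred just after the vaccination indicated by the visit number". Events before vaccination or "with a time of onset higher than defined above will not be included in analysis, but will be listed separately". SAP 4.4.1.3.2 applies the same onset method to SAEs but gives them a second, whole-study period. Non-serious AEs have no such second period.

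**Stop dates.** The footnote in Protocol 9.3.2.3.3 says "The stop date of all related AEs will be actively solicited"; for other events the investigator supplies the date when it becomes available. It adds: "AEs for which no stop date was obtained during the course of the trial will be considered as ongoing" at the end of the trial.

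**Window.** The protocol's synopsis, Sections 5.1.1, 5.1.3 and 9.3.2.2, and SAP 3.1 and 3.2 all run unsolicited AEs to Visit 2, which falls on Day 30 to Day 44. Protocol 9.3.2.3.3, in its heading and text, limits recording to 30 days. SAP 5.7 records no change to the planned analyses.

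**The concern.** The two onset rules cannot both be followed, because 4.4.1.2.4 is exclusive and its formula contains no stop date. Time of onset is part of the unsolicited AE endpoint (Protocol 9.3.2.2), and SAP 5.1.3.2 tabulates these AEs by the endpoint's categories. Losing known onset days therefore affects a planned output. Under 5.3.1.5, whether a late AE is tabulated or only listed depends on whether someone obtained a stop date, not on when the AE began. Two programmers, each following one section, could put the same AE in different outputs.

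The window is a second problem. Non-serious AEs that begin after Day 30 and by Visit 2 fall within the stated endpoint but reach no table. Where parents followed the 30-day instruction, such AEs may also be under-recorded.

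**Working it through.** The plan gives no figure to reproduce. The check applies both onset rules to test events and then counts days.

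**Inputs.** Day 0 is vaccination. Rule A (SAP 4.4.1.2.4): onset = start day, missing only if the start or the vaccination date is missing. Rule B (SAP 5.3.1.5): onset is missing if the start or the stop date is missing. Tabulation (SAP 4.4.1.2.4): onset 0 to 30 or missing is counted; onset below 0 or above 30 is listed only. The vaccination date is taken as known.

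| Start | Stop | Rule A | Rule B |
|---|---|---|---|
| D10 | D12 | onset D10, counted | onset D10, counted |
| D10 | none | onset D10, counted | onset missing, counted |
| D31 | D33 | listed | listed |
| D31 | none | listed | onset missing, counted |
| D40 | none | listed | onset missing, counted |

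For starts on Day 0 to 30 the 30-day count is the same under both rules; only the onset day is lost. The count changes for starts after Day 30 with no stop date.

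A start before vaccination with no stop date can shift in the same way. The text leaves a condition open here: "If an unsolicited non-serious AE has a non-missing visit number, the visit number should be used to determine the last vaccination", and the start date is used if the visit number is absent. With a visit number pointing to the study vaccination, the event is counted under rule B. Without one, its start date precedes vaccination, and the reading adopted here is that it is not assigned to the study vaccination and so not counted.

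**Time available to resolve.** The earliest onset after Day 30 is Day 31. The days from then to Visit 2 are:

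- Visit 2 on Day 31: 31 − 31 = 0
- Visit 2 on Day 37: 37 − 31 = 6
- Visit 2 on Day 44: 44 − 31 = 13

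An absent stop date is therefore plausible in the group whose placement changes.

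**Days outside the tables.** Follow-up covers Day 0 to Visit 2, that is V + 1 days for Visit 2 on Day V. The tables cover 31 days (Day 0 to 30). The untabulated share is (V − 30)/(V + 1):

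- V = 30: 0/31 = 0%
- V = 37: 7/38 = 18.4%
- V = 44: 14/45 = 31.1%

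These are shares of days, not of AEs.

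**The case against.** The case against giving this much weight is reasonable. Section 4.4.1.2.4 is the dedicated derivation, SAP 4.4.1.3.2 sends SAEs to it, and the start-or-stop condition is plainly the duration rule. An attentive programmer would suspect a slip. The 30-day count moves only for a narrow group of unknown size, and all safety analyses are descriptive. A fixed 30-day table gives subjects a common window and agrees with Protocol 9.3.2.3.3; Sections 6.7 and 11.1 also speak of a 30-day follow-up. Later non-serious AEs are listed, and SAEs have a whole-study period, so nothing is concealed.

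Much of this stands as a limit on size. The fixed 30-day table should remain the main one. The day shares do not measure harm, and 31% is the edge of the visit window. The pre-vaccination case is marginal. SAEs are probably unaffected: 5.3.1.5 says unsolicited AEs without qualification, but SAP 5.3.1.2 names SAEs separately when it means them.

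It does not remove the conflict. Section 5.3.1.5 is an explicit rule, and nothing in the SAP ranks it below 4.4.1.2.4. That an ongoing AE counts as having a missing stop date is an inference, but SAP 5.3.1.5 says missing stop dates are not imputed, so no date would be supplied. On the window, agreement with one protocol section leaves the SAP short of the endpoint in another. The additional 30-day references add to the inconsistency.

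**Conclusion.** Both parts hold. As written, SAP 5.3.1.5 contradicts SAP 4.4.1.2.4. If followed, it loses the onset day of every unsolicited AE without a complete stop date and moves some AEs that began after Day 30 into the 30-day table. A drafting slip carried over from the duration rule is the likely cause, but that is inference. Separately, the non-serious AE tables leave out up to 14 days of the protocol's endpoint window, and none when Visit 2 is on Day 30.

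The size in AEs is unknown, since the documents give neither AE rates nor rates of missing stop dates. The result assumes that an AE without a stop date is treated as having a missing one, and that Visit 2 falls within its window. The effect is confined to descriptive safety output. The correction should be made, but it does not bear on the non-inferiority conclusions.

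**What to change.** 1. Replace the sentence in SAP 5.3.1.5 so that onset is missing only when the AE start date or the vaccination date is missing or incomplete, and duration is missing when the AE start or stop date is missing or incomplete.
2. Keep the fixed 30-day table as the main one. Add a supplementary Day 0 to Visit 2 summary of unsolicited non-serious AEs, parallel to the whole-study period that SAEs already have.
3. Reconcile Protocol 9.3.2.3.3 with the synopsis and Sections 5.1.3 and 9.3.2.2. If collection is already over, as the past tense of SAP 3.1 suggests, state in SAP 5.7 that the protocol sections differ and which window each table uses.

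The cost is one sentence, one summary and some wording; no new data are needed. The supplementary window varies by up to 14 days between subjects, and recording after Day 30 may be incomplete where the 30-day instruction was followed. The summary may therefore undercount and should carry that caveat.

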5.3.1.6 Action Taken

Missing actions taken will remain missing and not be imputed.

5.3.2 Immunogenicity

Missing data will not be imputed. No test or search for outliers will be performed. In order to appropriately manage extreme values (undetectable responses $< \text{LLOQ}$ and $\geq [\text{ULOQ}]$), the following computational rule is applied to the values provided in the clinical database for each BL drawn for analysis purposes:

- If a value is $< \text{LLOQ}$, then use the computed value $\text{LLOQ}/2$
- If a value is between $\geq \text{LLOQ}$ and $< \text{ULOQ}$, then use the value
- If a value is $\geq \text{ULOQ}$, then use the computed value ULOQ

5.4 Interim / Preliminary Analysis

No interim / preliminary analyses are planned.

5.5 Determination of Sample Size and Power Calculation

[REDACTED]

[REDACTED]

[REDACTED]

[REDACTED]	[REDACTED]	[REDACTED]	[REDACTED]	[REDACTED]
[REDACTED]	[REDACTED]	[REDACTED]	[REDACTED]	[REDACTED]
[REDACTED]	[REDACTED]	[REDACTED]	[REDACTED]	[REDACTED]
[REDACTED]	[REDACTED]	[REDACTED]	[REDACTED]	[REDACTED]
[REDACTED]	[REDACTED]	[REDACTED]	[REDACTED]	[REDACTED]
[REDACTED]	[REDACTED]	[REDACTED]	[REDACTED]	[REDACTED]

[REDACTED]

[REDACTED]

[REDACTED]	[REDACTED]	[REDACTED]	[REDACTED]	[REDACTED]
[REDACTED]	[REDACTED]	[REDACTED]	[REDACTED]	[REDACTED]
[REDACTED]	[REDACTED]	[REDACTED]	[REDACTED]	[REDACTED]
[REDACTED]	[REDACTED]	[REDACTED]	[REDACTED]	[REDACTED]
[REDACTED]	[REDACTED]	[REDACTED]	[REDACTED]	[REDACTED]
[REDACTED]	[REDACTED]	[REDACTED]	[REDACTED]	[REDACTED]

[REDACTED]

5.6 Data Review for Statistical Purposes

A review of the data has been anticipated through the data review process led by data management before database lock. This review of the data included a statistical review.

